4.6.3 Safety Sample

Safety analysis will include all randomized patients.

4.7 Baseline patient characteristics

Baseline data will be described using mean and standard deviation, median and interquartile range, counts and percentages as appropriate. Baseline characteristics will include but will not be limited to

- Diagnosis (operative vs. non-operative)
- Subdiagnosis for non-operative subjects (respiratory, cardiovascular, other)
- Charlson comorbidity index and components
- APACHE score
- SOFA score
- Cumulative fluid balance
- Neuromuscular blockade
- Steroid use
- Antipsychotic use
- Baseline sedation category

5 Outcomes

5.1 Primary Outcome

The primary outcome is the time from randomization to successful liberation from invasive mechanical ventilation. Successful liberation is reached the moment IMV is discontinued, provided the subject remains alive and free of IMV for at least 7 days subsequently. In other words, the date of successful liberation is the date of the extubation (or disconnection from ventilator for patients with tracheostomy) that was followed by at least 7 ventilator-free days.

5.2 Secondary Outcomes

The secondary outcomes are

- 1. Ventilator-free days at day 14, 21 and 28 post randomization
- 2. Time from randomization to live ICU discharge (up to day 90)
- 3. Time from randomization to live hospital discharge (up to day 90)
- 4. Mortality, measured as time to death, ICU mortality; hospital mortality; 21, 28, and 90 day mortality
- 5. Weaning Progress, measured as time from randomization to: first SBT; first successful SBT; first extubation or equivalent for tracheostomized patients.
- 6. Weaning Difficulties: Subjects will be classified in the 5 following groups according the WEAN Safe classification (calculated as time from first SBT/extubation):
 - (a) Successful liberation less than 24 hrs
 - (b) Successful liberation greater than 24 hrs but less than 7 days
 - (c) Successful liberation greater than 7 days
 - (d) Unsuccessful liberation alive but remain ventilator dependent at day 90
 - (e) Died prior to successful liberation
- 7. Weaning Complications, measured as the number of patients
 - used non-invasive ventilation post-extubation
 - ventilated more than 7 days post randomization
 - ventilated more than 21 days from time of randomization
 - ventilated more than 21 days from time of intubation (prolonged MV group)
 - receiving tracheostomy post-randomization
 - requiring re-intubation (up to 7d after planned extubation)
- 8. Safety and Tolerance of modes
 - Number of patients ever requiring A/C mode post randomization
 - Number of patient-days requiring A/C mode post randomization
 - Frequency and severity of reported serious adverse events across groups
- 9. Co-interventions are also monitored, including sedatives and anti-psychotic medications.

5.3 Exploratory Outcomes

5.3.1 Status at 90 days

We will create a composite outcome to reflect status at 90 days. This outcome will be an ordinal outcome with the following categories listed from worse outcome to best outcome:

- 1 Died
- 2. Remaining on ventilation at any location
- 3. Not ventilated but remaining in hospital or ICU
- 4. Discharged from hospital not ventilated

5.4 Measurement and Units of Outcomes

All time intervals and durations will be measured in days (to the nearest 1/10 of a day) and calculated from the day and hour of randomization to the day and hour of the event (eg. day and hour of extubation, disconnection from invasive MV, ICU discharge, live hospital discharge, or death).

5.5 Calculation of ventilator-free days

"Ventilator-free days" (VFDs) are defined as the number of days alive and free of INVASIVE ventilation post SUCCESSFUL LIBERATION (successful extubation or successful termination of invasive MV for patients with tracheostomy). Non-invasive ventilation may be used post extubation, but is not counted as "invasive ventilation."

- If the patient dies before achieving successful liberation from invasive MV, that patient will have 0 VFDs.
- However, if a patient dies AFTER achieving successful liberation, that patient will have the number of VFDs counted as the number of days alive and free of invasive MV occurring between time of successful extubation/successful termination and time of death.

5.5.1 Assessment of Co-interventions

Co-interventions occurring during the study will be described as well as other patient characteristics that were collected during follow-up such as SOFA score, daily fluid balance, cumulative dose of sedating medications, number of patients and patient-days receiving any antipsychotic medication.

5.5.2 Sedating Medications and Sedation, Agitation, and Delirium Scores:

Sedating medications are routinely administered as part of routine ICU care, and may influence duration of IMV (reference). As such, they are co-interventions. However, a patient's requirement for sedating medications may be influenced by many factors, including acuity of illness, presence of delirium, pain, and patient-ventilatory dyssynchrony. Since patient-ventilator dyssynchrony may differ between PAV+ and PSV, mode of ventilation may influence amount of sedating medications administered, and amount of sedating medications administered may in turn influence duration of IMV. We will take the following approach to analyzing sedating medications and sedation, agitation, and delirium scores:

Drug conversions

- 1. Opioids daily total dose of all opioid medications will be converted to morphine IV equivalents [25, 26, 27]
- 2. Benzodiazepines daily total dose of all benzodiazepine medications, propofol and dexmedetomidine will be converted to midazolam IV equivalents [28] [26]

3. Other sedative infusions – we had planned to analyze propofol, dexmedetomidine, and ketamine separately; however, a recent study [28] described a method for converting propofol and dexmedetomidine to midazolam equivalents based on "expert opinion and clinical practice;" we will use their conversion factor to convert propofol and dexmedetomidine to midazolam equivalents and include in the total daily dose of midazolam IV equivalents. Ketamine will be analyzed independently.

Drug doses will be compared across groups using mixed effects models adjusted for baseline and with a time by treatment interaction term.

The number of patients and number of patient-days receiving any antipsychotic medication will be compared between groups.

Sedation/agitation scores

Different scoring systems were used across institutions to assess the level of sedation or agitation and included the Richmond Agitation Scalation Score (RASS), the Riker Sedation-Agitation Scale (SAS), or the Ventilator-Adjusted Motor Activity Assessment Scale (VA-MAAS). Sedation was scored twice daily (morning score and highest daily score) using whatever scale was in use at each participating centre. Each score will be analyzed separately, and scores will be converted to 4 categories using the following conversion table derived from Khan et al 2012[29], and analyzed descriptively.

Category	RASS	VAMASS	SAS
Moderate to deep sedation	-3 to -5	0 to 1	1-2
Light sedation	-2 to -1	2	3
Alert and calm	0	3	4
Restless/Agitated	+1 to +4	4 to 6	5 to 7

Delirium score

Delirium category will be assessed in a subset of patients where data is available using a combination of two scoring systems: the Confusion Assessment Method for the ICU (CAM-ICU) and the Intensive Care Delirium Screening Checklist (ICDSC) values as follows:

- 1. Delirium not assessed: either missing data or marked as not assessed in database
- 2. Too sedated to assess = Coma
- 3. Delirious (CAM-ICU positive, ICDSC 4-8)
- 4. Not delirious (CAM-ICU negative, ICDSC 0-3)

The delirium category will be described over the study period for each group.

6 Analysis methods: Frequentist Analysis

6.1 Primary Outcome

The primary outcome of time to successful liberation from mechanical ventilation will be summarized using cumulative incidence curves with death considered to be a competing risk. Cumulative incidence will be compared across groups using Gray's test.

6.1.1 Primary Analysis

Treatment effect will be reported as a hazard ratio with 95% confidence interval. The primary analysis will use a mutistate generalization of the Cox proportional hazard model. This approach simultaneously models the association between treatment and all transitions in the model. Missing outcome data will be treated as censored at the date of last contact.

PAV
PSV

Weaning Criteria
SBT/TMT
Extubation/Disconnection

Liberated, in ICU

ICU Discharge

Liberated, in hospital

Hospital Discharge

Liberated, home

Death

Dead

Figure 3: State transition diagram

Figure 3: State transition diagram

IMV = invasive mechanical ventilation; SBT = spontaneous breathing trials; TMT =tracheostomy mask trials; ICU = intensive care unit

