9.2 Outcome Measures and Duration of Follow-up

Liberation from invasive mechanical ventilation is achieved at the moment of “successful extubation” for patients with an endotracheal tube, or at the moment of “successful termination of invasive MV” for patients with a tracheostomy tube.

For patients with an endotracheal tube, “**successful extubation**” is defined as removal of the endotracheal tube AND remaining alive with no need for reintubation/reinstitution of invasive mechanical ventilation for 7 days post extubation, or until successful ICU discharge, or until live hospital discharge, whichever comes first.

For patients with a tracheostomy tube, “**successful termination of invasive MV**” is defined as having the tracheostomy tube disconnected from the ventilator AND remaining alive with no need for reinstitution of invasive MV for 7 consecutive days, or until successful discharge from ICU, or until live hospital discharge, whichever comes first.

“**Successful ICU discharge**” is defined as leaving the ICU where the patient was receiving invasive MV, AND remaining alive with no need for reinstitution of invasive MV AND no need for readmission to ICU within 48 hours of ICU discharge.

“**Ventilator-free days**” (VFDs) are defined as the number of days alive and free of INVASIVE ventilation post SUCCESSFUL EXTUBATION or post successful termination of invasive MV. Non-invasive ventilation may be used post extubation, but is not counted as “invasive ventilation.” If the patient dies before achieving successful extubation or successful termination of invasive MV, that patient will have 0 VFDs. However, if a patient dies AFTER achieving successful extubation, successful termination of invasive MV, or successful ICU discharge, that patient will have the number of VFDs counted as the number of days alive and free of invasive MV occurring between time of successful extubation/successful termination and time of death.

All time intervals and durations will be measured in days (to the nearest 1/10 of a day) and calculated from the day and hour of randomization to the day and hour of the event (eg. day and hour of successful extubation, successful termination of invasive MV, successful ICU discharge, live hospital discharge, or death).

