6.1.2 Secondary Analyses

A secondary analysis will be performed using a cause-specific Cox model to model the treatment effect on successful liberation with death prior to successful liberation treated as a censoring event.

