7.2 Bayesian Analysis of Primary Outcome

The primary outcome (time to successful liberation, in ICU from mechanical ventilation) will be analyzed using accelerated failure time (AFT) models. These differ from the proportional hazards models that will be used in the primary frequentist analysis (section 5.6.1) because they require distributional assumptions for the hazards. AFT models are better suited to this context because Bayesian methods assume that all parameters have a distribution. These models will estimate time ratios, which can be interpreted as the multiplicative effect of a covariate on survival time.

As specified in the primary frequentist analysis, each transition in Figure 3 will be modelled. To maximize model flexibility, each transition will be fit to a separate AFT distribution [34]. For each transition, we will select the best model among exponential and Weibull AFT families. The model with the lowest AIC will then be modeled in INLA [35, 36].

Semi-Markov modelling will be implemented, based on clinical knowledge that the probability of transitioning would depend on the time spent in each state. For these models, time will reset to 0 when patients enter each new state.

7.2.1 Informative Prior Treatment Distribution for the Transition Between Invasive Ventilation to Liberated, In ICU

We will use an informative prior for the treatment effect on the transition between invasive ventilation to liberation, in ICU. To determine the prior, we assumed that the number of ventilator-free days in the baseline dataset would roughly correspond to the time that patients were freed from ventilation. Patients with 28 ventilator-free days were considered freed on day 0. These patients were assigned a time of 0.001, as only non-zero times could be included in AFT models. For patients with 1 to 27 ventilator-free days, the difference between 28 days and the number of ventilator-free days was considered the time to being freed from ventilation. Patients who died or started off-ventilator were excluded.

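### Liberation is dated at extubation but granted only after 7 days' survival, so the death transitions out of the Liberated states need delayed entry and a stated time scale; the primary hazard ratio is not affected

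*SAP*

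**What the plan says.** SAP 5.1: "Successful liberation is reached the moment IMV is discontinued, provided the subject remains alive and free of IMV for at least 7 days subsequently". It gives no exception.

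Protocol 9.2 lets the 7 days end early: "or until successful ICU discharge, or until live hospital discharge, whichever comes first". A successful ICU discharge there also requires survival without invasive ventilation and "no need for readmission to ICU within 48 hours of ICU discharge".

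SAP 6.1.1 makes a multistate generalization of the Cox model the primary analysis: "This approach simultaneously models the association between treatment and all transitions in the model". The legible Figure 3 labels include three Liberated states (in ICU, in hospital, home) and Dead. The section does not state a time scale and does not say how the 7-day window is handled.

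SAP 6.1.2 adds a cause-specific Cox model with "death prior to successful liberation treated as a censoring event".

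SAP 7.2 carries the structure into the Bayesian analysis: "As specified in the primary frequentist analysis, each transition in Figure 3 will be modelled". Each transition gets its own accelerated failure time model, exponential or Weibull, and "For these models, time will reset to 0 when patients enter each new state". SAP 7 undertakes to report posterior summaries for every model parameter.

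**The concern.** Entry to a Liberated state is fixed by what happens over the following week. A patient extubated on day 5 who dies, still extubated, on day 9 never enters that state and is counted as dying before liberation. Two things follow for the death transitions.

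- The time at risk of death after liberation includes a first week in which no death can be recorded.
- Early post-extubation deaths move to the transition from invasive ventilation to Dead.

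An excess of early post-extubation deaths in one arm would therefore look like an excess on the ventilator, and never like post-liberation mortality. SAP 5.5 expects deaths after liberation, and Protocol 6.4 makes mortality a safety endpoint, so readers may well interpret these transitions.

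**Working it through.** **The plan's own figures.** The documents give no figure for any death transition. The related figures reproduce: events for HR 1.30 are 4 × (1.960 + 0.842)² / (ln 1.30)² = 456.1, against 456 stated in Protocol 12.1 and SAP 2.3.

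**Inputs from the documents.**
- Liberation hazards: ln 2 / 7.70 = 0.0900 per day (PSV) and ln 2 / 5.92 = 0.1171 per day (PAV+).
- Proportion liberated: 456 / 529 = 86.2%, leaving 13.8% who die first. A ventilated death hazard of 0.0163 per day matches this: 0.0900/0.1063 = 84.7% and 0.1171/0.1334 = 87.8%, mean 86.2%.

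**Assumptions, not in the documents.** Post-extubation death hazard h of 0.003 to 0.006 per day, equal in both arms; exponential ICU stay after extubation with mean s of 3 or 5 days. A wider set uses h up to 0.012 in the first week, 7-day reintubation of 10% to 20%, and median ICU stays of 2 to 5 days.

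**1. Death-free share of in-ICU liberated time:** 1 − exp(−7/s).
- s = 3: 1 − exp(−2.33) = 90%.
- s = 5: 1 − exp(−1.40) = 75% (76% when simulated with the day-90 limit).
- Medians of 2, 3 and 5 days: 1 − 2^(−7/m) = 91%, 80% and 62%.

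**2. Fitted in-ICU death rate, exponential, clock reset.** All recorded deaths fall after day 7 but all the time is counted, so the rate is about h × exp(−7/s): 0.097h for s = 3 and 0.247h for s = 5. Simulation gives about 10% and 24% of the true rate. For medians of 2, 3 and 5 days and h = 0.006, the fitted rates are 0.0005, 0.0012 and 0.0022 per day. No Weibull hazard can be zero for 7 days and positive afterwards either.

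**3. Deaths moved to death before liberation:** 0.862 × (1 − exp(−7h)).
- h = 0.003: 0.862 × 0.0208 = 1.8% of patients, about 10 of 558.
- h = 0.006: 0.862 × 0.0411 = 3.5%, about 20 of 558.

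Against 13.8%, that is 13% to 26% more deaths on this transition. The wider set, with reintubation, gives 9 to 42 per 558, or 9% to 31% of all deaths counted there. With no effect of mode on any death hazard, the simulated ventilated-to-dead hazard ratio is 1.03 to 1.08, because the arm extubated faster contributes more of these deaths.

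**4. Cox hazard ratio, *Liberated, in ICU* to Dead (simulated).**

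| Time scale and entry | True 1.00 | True 0.70 |
|---|---|---|
| From randomization, entry at extubation | 1.10–1.14 | 0.78–0.82 |
| From randomization, entry at +7 days | 0.95–0.99 | 0.66–0.70 |
| Clock reset | 0.95–0.99 | 0.66–0.70 |

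On the randomization clock, PSV patients are liberated later, so at a given day more of them are still in the death-free week. That pushes the ratio toward apparent harm from PAV+. The 0.95 comes from the setting with fewest deaths: 0.58 per 558 among 4 million patients is about 4,200 deaths, standard error of the log ratio about 2/√4,200 = 0.03, so it lies within simulation error of 1.

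**5. Primary contrast.** An extubation hazard ratio of 1.30 gives a ventilated-to-liberated ratio of 1.27 to 1.31. The small shift comes from failed extubations, not from the 7-day window. With treatment as the only covariate, this ratio equals the cause-specific one of SAP 6.1.2.

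**6. The two definitions.** Under the SAP rule, simulated deaths within 7 days of liberation are zero. Under Protocol 9.2 they are zero in the ICU, but about 1.5 to 5 per 558 occur after ICU discharge.

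**The case against.** A reader might infer that nobody can die in the week after liberation, that every death transition is wrong as fitted, and that the trial's mortality findings are at risk. The documents do not support that.

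- SAP 6.1.1 promises one treatment hazard ratio, for liberation, and it is sound. Sample size and power rest on it.
- Time to death is analysed from randomization by Kaplan–Meier and log-rank (SAP 6.2), alongside ICU, hospital and fixed-day mortality (SAP 5.2). None of these uses the liberation states, so early post-extubation deaths count in full.
- Under Protocol 9.2 the death-free week is absolute only while the patient stays in the ICU.
- The arrows of Figure 3 were not legible in the text available, so the Liberated-to-Dead transitions are inferred from the labels.
- With a clock reset, no death falls in the window, so the Cox hazard ratio for deaths after day 7 is the same with or without delayed entry.
- SAP 6.1.2 already names the competing event correctly. The 48-hour sensitivity analysis (SAP 6.6) shortens the window to 2 days, and time to first extubation (SAP 6.2) carries no 7-day condition.
- In-ICU deaths after day 7 are few, about 0.5 to 6 per 558, so that transition is barely estimable however it is set up.

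All of this stands, and it limits the point to the death transitions. It does not remove the point. The Cox time scale is unstated, and one natural choice distorts the ratio. The Bayesian clock is stated, the family is wrong for these transitions, and the parameters are to be reported. SAP 7.2.1 allows for another family fitting better, but only for the ventilated-to-liberated transition. Because each transition is modelled separately, the liberation time ratio is not touched.

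**Conclusion.** The concern holds for the post-liberation death transitions and for the meaning of the ventilated-to-dead transition, and no further. It is clearest in SAP 7.2, where an exponential fit would give about 10% to 24% of the true in-ICU death rate for mean stays of 3 to 5 days. Those percentages depend almost wholly on the assumed ICU stay and hold under either definition, since a patient still in the ICU must survive the full 7 days. Across all Liberated states the understatement is about 9% to 11% for h of 0.003 to 0.006, under the SAP wording only.

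In SAP 6.1.1 the in-ICU death hazard ratio would read about 1.10 to 1.14 for a true 1.00 if time runs from randomization. Over all Liberated states to day 28 the bias is smaller, about 1.03 to 1.04. If the clock resets, the ratio is sound for deaths after day 7 and silent on earlier ones.

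This should be settled before analysis because the death transitions could mislead. The primary result is not in question.

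**What to change.** 1. Reconcile SAP 5.1 with Protocol 9.2 and state one rule for when liberation is confirmed. Protocol 8.3.6 gives a further variant for tracheostomized patients and should be included.
2. State the time scale of the multistate Cox model in SAP 6.1.1.
3. For every Liberated-to-Dead transition, in both the Cox and the Bayesian models, start risk when the confirmation window closes, by delayed entry. Under the SAP rule that is extubation or disconnection plus 7 days.
4. Label the other death transition as death before successful liberation, as SAP 6.1.2 does, and report by arm how many of those deaths followed extubation.

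**Cost.** SAP wording and an entry time in the model data set; Protocol 9.1 and 9.2 already collect the dates. Delayed entry removes most in-ICU liberated time from the risk set (75% to 90% for mean stays of 5 to 3 days), so that transition will be very imprecise and should be reported as such. No post-liberation deaths are lost under the SAP rule. If the protocol rule is adopted, a fixed 7-day entry would drop about 1.5 to 5 early post-discharge deaths per 558, so entry should then follow each patient's own window end.

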6.1.2 Secondary Analyses

A secondary analysis will be performed using a cause-specific Cox model to model the treatment effect on successful liberation with death prior to successful liberation treated as a censoring event.

6.2 Secondary Outcomes

The outcomes related to weaning progress and difficulties (listed below) also suffer from the competing risk of death and other improper subgroup issues. and will be looked at primarily descriptively.

- Time to death: will be analyzed using standard methods for survival data namely Kaplan-Meier curves and log-rank test. Treatment effects will be reported as hazard-ratios with 95% confidence intervals.
- Time from randomization to live ICU discharge (up to day 90) and time from randomization to live hospital discharge (up to day 90): Those two outcomes both have death as a competing risk. Cumulative incidence curves will be constructed to provide estimates of live ICU discharge and live hospital discharge that account for death. Cause-specific treatment effects on live ICU discharge and live hospital discharge will be reported as hazard ratios with 95% confidence intervals from Cox proportional hazard models.
- Time from randomization to first SBT, first successful SBT, and first extubation: These will be looked at primarily descriptively using cumulative incidence curves with death as a competing risk and compared across groups using the Gray's test.

• Ventilator-free days:

Ventilator-free days will be compared across groups using a Wilcoxon test. The treatment effect will be expressed as the difference in median ventilator-free days and its 95% confidence interval will be estimated using bootstrap methods. As per the calculation above, subjects might have 0 ventilator-free days because either they died before being liberated or they survived but remained ventilated. We

will model this using a number of approaches. For the primary analysis, we will assign the value -1 ventilator free days to subjects who died prior to liberation.

The following secondary analyses are also planned to help understand any observed treatment effect.

- Assigning the value of zero ventilator-free days to patients who died prior to being liberated from ventilation and performing a Wilcoxon test
- Poisson regression of the number of days on ventilator with the logarithm of the number of days observed as an offset
- Marginal structural model where first the probability of surviving will be modeled and then the
 weighted analysis of the survivors will be carried out using the inverse of the survival probability
 as the weight
- Invasively ventilated with tracheostomy and invasively ventilated with ETT
- Number of patients successfully liberated in less than 24 hours since first SBT or first extubation attempt, number successfully liberated greater than 24 hours but less than 7 days, successfully liberated greater than 7 days, unsuccessful liberation (alive but remaining ventilator dependent at day 90), died prior to successful liberation. These outcomes will be compared across groups using the Chi-Square or Fisher's exact test.
- Delirium and sedation scores: Daily sedation scores will be analyzed as described in Section 5.5.2.
- Number of patients who received non-invasive ventilation post-extubation, ventilated more than 7 days post randomization, ventilated more than 21 days from time of intubation (prolonged MV group); receiving tracheostomy post-randomization, requiring re-intubation (up to 7d after planned extubation): These outcomes will be compared across groups using the Chi-Square or Fisher's exact test.
- Number of patients ever receiving A/C mode post randomization (Tolerance of modes): This outcome will be compared across treatment groups using Chi-Square or Fisher's Exact test and treatment differences will be reported as an odds ratio with 95% confidence interval. Patients not receiving A/C will be assigned a value of zero days. The non-parametric Wilcoxon rank-sum test will be favoured over the parametric t-test for this analysis if there are many zero days entries.

